19.2 STATISTICAL ANALYSIS POPULATIONS

All analyses will be conducted on the intention-to-treat (ITT) population and carried out at a 2-sided 5% level of significance. The ITT population is defined as all patients randomised to treatment regardless of non-compliance, loss to follow-up, or death.

The secondary endpoint analysis, incidence of cirrhosis in non-randomised patients, will be conducted on follow-up data from those patients who registered and consented to the trial, but who were not randomised due to having an ELF score of < 8.4 (see section 6.3).

Attempts will be made to retrieve missing data via a thorough data cleaning process.

19.2.1 Primary endpoint analysis

Incidence and timing of severe complications of cirrhosis will be calculated from the date of randomisation to the occurrence of the first event (severe complication). Cirrhosis is diagnosed either by, having an ELF score ≥ 9.5 in the ELF arm or in the control arm, via standard methods. An 'event' encompasses variceal haemorrhages, spontaneous bacterial peritonitis, unresectable hepatocellular cancer, encephalopathy (grade 3 or 4) and liver

related mortality. Cox regression analysis, adjusting for the minimisation factors (see section 12.2), will be used to compare the differences between the control and ELF arm. Overall survival curves will be calculated using the Kaplan-Meier method, hazard ratios and corresponding 95% confidence intervals will be presented.

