4.4.6 ELF

The Enhanced Liver Fibrosis (ELF) test is a CE marked (EU Regulatory Approved) test for liver fibrosis that has been developed over a decade in a cohort of over 1,000 patients and subsequently validated in thousands more. The test has been shown to accurately reflect the severity of liver fibrosis in a wide range of chronic liver diseases, at all stages of liver fibrosis.

The test can detect mild and moderate degrees of fibrosis accurately although performance is best in the detection of advanced fibrosis and cirrhosis; in patients with Chronic Hepatitis C area under the curve (AUC) receiver operating characteristic curves (ROCs) of 0.85 for 0-3 vs. 4-6 and 0.87 for 0-4 vs. 5-6 Ishak stages respectively, and in patients with NAFLD, AUC ROCs of 0.90 and 0.82 for severe fibrosis and moderate fibrosis^{34,35}. Analysis of the risk of liver-related complications in a cohort of 500 patients with CLD followed over a period of 7 years revealed that an increase of 1 unit in the ELF score correlated with a doubling of the risk of liver-related events³⁶.

Analysis of data from studies of ELF shows that ELF correlates with severity of liver fibrosis as determined by liver biopsy and fibroelastography. The long-term follow-up of patients enrolled in the original ELF study revealed that ELF scores at baseline predict the incidence of liver related events as well as mortality³⁵. The ELF scores of patients whose liver biopsies have been classified using widely accepted Ishak fibrosis staging system suggest the categories in Table 1.

Table 1. ELF scores and fibrosis staging.

Fibrosis stage (Ishak)	ELF Range³⁵
Normal/Mild (F0-F2)	<8.37
Moderate (F3)	8.37-8.73
Moderate/Severe (F4)	8.74-9.12
Severe (F5)	9.13-9.49
Cirrhosis (F6)	≥9.5

However this categorisation undervalues the performance of serum markers by converting linear variables into categorical ordinal variables.

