12.2 RANDOMISATION

**PLEASE NOTE THAT THE RANDOMISATION LINE IS DUE TO CLOSE
30/04/2013.**

**RANDOMISATIONS MUST BE PERFORMED BY THIS DATE. IF THIS IS
NOT POSSIBLE, PLEASE DISCUSS SPECIFIC CASES WITH CTRU.**

Following receipt of the results of the registration ELF test, patients who fulfil the eligibility criteria for randomisation (section 7.2) will be randomised on a 1:1 basis to 'screening for cirrhosis with ELF' or 'screening for cirrhosis with standard care'. Patients who are above the threshold for randomisation should be seen following receipt of the results of the registration blood tests (including ELF testing) as soon as possible and preferably within 6 weeks of the registration visit, but up to 12 weeks is permissible. However, if there is likely to be a delay in excess of 6 weeks please contact the CTRU to discuss.

Patients should also be asked to arrive fasted for this visit to allow for Glucose \pm HOMA-IR testing. For trial purposes, a patient is considered fasted if they have gone without food either overnight or for more than 4 hours. During this fasted period, however, the consumption of water is allowed.

A computer-generated minimisation program that incorporates a random element will be used to ensure treatment groups are well-balanced for the following characteristics (details of these stratification factors will be required for randomisation):

- Centre
- Age (≥ 18 to < 40 , ≥ 40 to < 65 and ≥ 65 to < 75)
- Gender (Male, Female)
- Baseline ELF score:
(≥ 8.4 to < 9.5 , ≥ 9.5 to < 11.5 ≥ 11.5 to < 12.5 and ≥ 12.5)
- History of high alcohol consumption (at any time), defined as > 6 units*/day for 12 months or more for males and > 4 units/day for 12 months or more for females (Yes, No)
- Current alcohol consumption per day (Males: 0 units (teetotal), < 3 units (light), 3-6 units (moderate), > 6 units (high); Females: 0 (teetotal), < 2 units (light), 2-4 units (moderate), > 4 units (high))
- Type of CLD (ALD, Viral, Unknown/Other, NAFLD)

*one unit is defined as 10 grams of alcohol

Randomisation will be performed centrally using the CTRU automated 24 hour telephone registration system. Authorisation codes and PINs, provided by the CTRU, will be required to access the registration system.

The following information will be required at randomisation:

- Unique authorisation and PIN code
- Name of person randomising patient
- Patient trial number (from registration)
- Confirmation of continued eligibility
- Patient's date of birth

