- Patient's gender
- Patient's baseline ELF score (information will be input by CTRU)
- Patient's alcohol consumption (past and current)
- Type of CLD
- Confirmation of randomisation visit health questionnaires completion (EQ-5D™, SF-12v2™, and Health Usage Questionnaire)

Direct line for randomisation [name]

The randomisation system will allocate the patient's trial number and randomisation result: routine clinical monitoring or routine clinical monitoring plus ELF monitoring. Where patients are randomised to routine clinical monitoring plus ELF monitoring the randomisation system will also instruct

whether the ELF score indicates the patient should commence the management and treatment of cirrhosis.

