Eighty out of the first 225 (37%) patients have presented with an ELF >9.49 . We are aiming to recruit 500 patients per arm, so we would expect 185 control arm patients to have an ELF >9.49 . With a 22% incidence rate of severe complications at 36 months, 24 months of recruitment and 30 months of follow up the expected number of events in these 185 patients can be calculated, using the method described by Collett⁴⁴ for sample size estimates based on exponential survival distributions (more details of which can be seen in the SAP). This produces an estimate of 46.4 events in these 185 control arm patients. We would also expect approximately 10% of the remaining 315 control arm patients to progress to cirrhosis on clinical grounds and to subsequently have a similar probability of then developing severe complications. This adds another 5.1 estimated events from this group, giving a total of approximately 52 estimated events in the control arm. We expect to reduce this number by 40% in the ELF arm, giving a total number of estimated events in this arm of 31. The median survival times, assuming negative exponential survival distributions, that would produce these numbers of events for the control and ELF arms with 24 months of recruitment and 30 months of follow up are 22.5 and 39.1 years, respectively. These figures can be used to calculate the power to detect such an effect size, which, with a type I error rate of 5%, gives a figure of 70%. However, if follow-up is continued until five years beyond the end of the programme grant, i.e. 69 months of follow-up rather than 30, the power to detect this effect size increases to just over 90%.

To calculate the power, with these 1000 patients, to detect a difference in the secondary endpoint of numbers of patients encountering severe complications subsequent to being detected with cirrhosis, we also need to estimate the numbers of patients developing cirrhosis in the two arms. We expect approximately 10% of the 315 patients with an ELF score between 8.4 and

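### The adjusted Cox models, read plainly, use baseline ELF only as four wide bands; adding the continuous score alongside the bands would recover a little power

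*Protocol*

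**What the plan says.** Section 19.2.1 sets the primary analysis as "Cox regression analysis, adjusting for the minimisation factors (see section 12.2"). Section 19.2.2 adjusts for the same factors in three secondary analyses: severe complications from diagnosis of cirrhosis, time to diagnosis of cirrhosis, and detection of complications.

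Section 12.2 lists the factors. Their stated purpose concerns allocation: the minimisation program "will be used to ensure treatment groups are well-balanced for the following characteristics". "Baseline ELF score" appears there as four bands, cut at 9.5, 11.5 and 12.5. The same section lists among the randomisation inputs "Patient's baseline ELF score (information will be input by CTRU"), so the score itself is held for every randomised patient.

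Section 4.4.6 reports that "an increase of 1 unit in the ELF score correlated with a doubling of the risk of liver-related events". It also says, of the Ishak staging categories in Table 1, that such a categorisation "undervalues the performance of serum markers by converting linear variables into categorical ordinal variables".

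The protocol does not say how each factor is coded in the Cox model. Section 19 leaves further detail to the SAP, which is not at hand.

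**The concern.** Bands chosen to balance allocation need not be the best form of a covariate. If risk rises smoothly with ELF, two patients at opposite ends of the 9.5 to <11.5 band differ about 4-fold in risk, yet the model treats them as alike. Chance imbalance between arms within a band then goes uncorrected, and some of the power available from a known predictor is lost.

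The trial has little power to spare. It closes at about 700 patients rather than 1000, and section 18.1 expects about 80% power for the primary endpoint only after five further years of follow-up. The top two bands may also be nearly empty, which makes their coefficients unstable.

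**Working it through.** **1. The plan's own power figures.** Inputs from section 18.1: medians of 22.5 and 39.1 years, 500 per arm, 24 months of accrual (A), 30 months of follow-up (F), two-sided 5%. With rate λ = ln 2 / median and uniform accrual,

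P(event) = 1 − [exp(−λF) − exp(−λ(F+A))] / (λA).

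This gives 51.0 + 30.1 = 81.1 events. The hazard ratio (HR) is 22.5/39.1 = 0.575. Schoenfeld power is Φ(√(81.1/4) × |ln 0.575| − 1.96) = 70.1%, against the stated 70%. With 69 months there are 150.2 events and power is 91.0% (Freedman) or 92.3% (Schoenfeld), against just over 90%. With 700 patients and 69 months there are 105 events and power is 80.9%, against about 80%. None of these calculations uses covariates, so the point changes none of them.

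**2. Spread of risk within a band.** At a doubling per unit, the risk ratio across a band is 2^width:
- 8.4 to 9.5: 2^1.1 = 2.1
- 9.5 to 11.5: 2^2 = 4

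**3. Patients per band.** The protocol gives only the split at 9.5: "Eighty out of the first 225 (37%) patients have presented with an ELF" above 9.49 (80/225 is in fact 35.6%). The shape beyond that is assumed. A truncated normal (mean 8.28, SD 1.28) was fitted to two figures: 1000/2160 registered patients at or above 8.4, and 37% of those at or above 9.5. It puts 63%, 36%, 1.2% and 0.1% in the four bands. A heavier tail (8.4 plus an exponential) puts 3.6% and 2.5% in the top two. The bands keep about 75% and 85% of the ELF variance respectively.

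**4. Power if log-hazard is linear in ELF.** Simulated Cox trials: true HR 0.575, allocation balanced within bands, other factors omitted, 3000 to 4000 trials per row, simulation error about 0.7 to 0.9 point.

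| Setting | No ELF | Bands | Linear only | Bands + linear |
|---|---|---|---|---|
| 1000 patients, 30 months, about 83 events, HR 2 per unit, truncated normal | 66.7% | 68.4% | 68.9% | 69.0% |
| Same, heavy tail | 61.1% | 68.3% | 70.9% | 70.3% |
| Same, truncated normal, HR 3 per unit | 63.1% | 67.1% | 69.2% | 69.1% |
| 700 patients, 69 months, about 111 events, HR 2 per unit, truncated normal | 79.9% | 81.3% | 82.2% | 82.2% |

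The bands already recover most of what a linear term offers. In the first row, before rounding, the share is (68.44 − 66.67)/(68.88 − 66.67) = 80%; in the other rows it is about 60% to 75%. Mean estimated HRs are 0.572 to 0.579 with bands and 0.567 to 0.574 with linear ELF. At most 8 fits per setting that used the bands failed to converge, which fits nearly empty top bands.

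**5. Power if risk steps at 9.5.** Section 18.1 plans 46.4 control events among 185 patients above 9.49 (46.4/185 = 25.1%) and 5.1 among the other 315 (5.1/315 = 1.6%). That is a contrast of about 15-fold, with 46.4/51.5 = 90% of control events above the cut. Smooth doubling under the truncated normal puts only about 60% there. Simulating the step with 700 patients and 69 months, under assumed ELF distributions, gives bands v linear-only of 78.1% v 73.3% and 79.1% v 74.7%, losses of 4.8 and 4.4 points. Further runs of the step with the top two bands merged, at both trial sizes and under two distributions, gave losses of 2.5 to 6.4 points.

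**6. Bands plus the continuous score.** In six further simulated settings this matched or beat bands alone, by 0.1 to 3.2 points. Where the hazard had both the jump at 9.5 and doubling per unit, the gain was 1.8 to 3.2 points. From the table above, the gains are 0.6, 2.0, 2.0 and 0.9 points.

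**The case against.** The strongest reply is that this is SAP detail. Section 19.2.1 names the covariates and not their coding, and adjusting for the minimisation factors is standard and valid. That stands in part. The protocol does fix the adjustment set, and the only form in which it lists ELF as a factor is the four bands, but the SAP may add a continuous term.

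A reader might infer that the protocol contradicts itself, because section 4.4.6 criticises categorising ELF. It does not. That remark concerns the staging categories of Table 1, not the minimisation bands or the Cox model. It supports the principle only.

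A reader might also infer that a linear term should replace the bands at no cost. The documents do not support this. The gain from linear-only adjustment appears when the simulated hazard is log-linear, which makes that model correct by construction. The protocol's own event split is close to a step at 9.5, where the swap loses power. For time to diagnosis of cirrhosis, section 12.3 makes an ELF score of 9.5 or more the diagnosis itself in the ELF arm, so risk jumps there by definition.

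It is also fair to say that the effect is small: several individual gains lie within simulation error.

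**Conclusion.** A minor, low-cost improvement. On the plain reading, the adjusted Cox models discard within-band information in a score that is already held for every randomised patient. The cost is roughly 0 to 3 points of power, with no material bias and no change to any stated sample size or power figure.

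The size rests on assumptions that the protocol does not supply: the ELF distribution above 8.4, the shape of risk across ELF, and the omission of the other minimisation factors from the simulations. The direction is more secure than the size: bands plus the continuous score did at least as well as bands alone in every setting examined. The documents do not show that the banded analysis is wrong, that the trial's power is misstated, or that ELF should enter as a linear term alone.

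**What to change.** Add one sentence to section 19.2, before any unblinded comparison is seen: the adjusted Cox models keep the banded ELF minimisation factor (at least the cut at 9.5, with the top bands merged if sparse) and also include baseline ELF as a continuous covariate. The bands stay as they are for minimisation. If the SAP already specifies this, the protocol need only be aligned with it.

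The cost is one extra model parameter and no new data.

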14.5 CESSATION OF FOLLOW-UP

Cessation of follow-up should only occur under the following circumstances:

- Patient has completed the final follow-up visit at 30 months post-randomisation
- Patient undergoes liver transplantation
- Patient has an episode of severe encephalopathy of (Westhaven criteria 3-4) or otherwise loses capacity to consent
- Patient dies
- Patient withdraws from trial

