16.3 LONG TERM ECONOMIC EVALUATION

The clinical trial outcome and resource utilisation data will be used to update the parameters of the pre-existing life time horizon cost effectiveness model. The model will then be used to calculate the expected incremental cost effectiveness ratio ELF guided detection and management, using a lifetime horizon.

Perspective and discounting will be consistent with the methods of primary within trial analysis.

Parameter uncertainty will be examined using Monte Carlo simulation. Results of the probabilistic sensitivity analysis (PSA) will be presented as the expected incremental cost effectiveness ratio; a scatter plot on the cost effectiveness plane and as a cost effectiveness acceptability curve (CEAC). The Expected Net Benefit of ELF guided detection and management will be calculated for a range of values of lambda, including £5,000, £15,000, £20,000 and £30,000; reflecting the work of Martin and colleagues³⁹.

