17 ENDPOINTS

17.1 PRIMARY ENDPOINT

- Time from randomisation to occurrence of first severe complication

Severe complications are defined by:

1. Variceal haemorrhage confirmed by one of the following:
 - a) visualisation through endoscopy
 - b) imaging
 - c) post-mortem
2. Spontaneous bacterial peritonitis:
Ascites confirmed by:
 - a) Imaging and/or
 - b) aspiration*and* infection confirmed by:
 - a) microscopy and/or
 - b) culture
3. Hepatocellular cancer (HCC) beyond the Milan criteria^{* 40, 41}
N.B. For the purposes of the trial cases of HCC falling within the Milan criteria are not regarded as endpoints as they are regarded as treatable.
4. Encephalopathy - grade 3 or 4 defined using the Westhaven criteria (Appendix 1)⁴².
5. Liver-related mortality. Any of the following:
 - a) Any mention of liver disease in part one of the death certificate
 - b) death due to hepatocellular cancer (HCC)
 - c) death due to liver failure
 - d) death due to bleeding from portal hypertension
 - e) death due to hepato-renal syndrome
 - f) death due to sepsis occurring as a result of chronic liver disease
 - g) death due to spontaneous bacterial peritonitis
 - h) death due to encephalopathy

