19.2.2 Secondary endpoint analysis

Incidence and timing of severe complications of cirrhosis from the date of diagnosis of cirrhosis (in clinic, date of clinic visit or blood sample) will be analysed using Cox regression analysis, adjusting for the minimisation factors (see section 12.2), and will be used to compare the differences between the control and ELF arm. Overall survival curves will be calculated using the Kaplan-Meier method, hazard ratios and corresponding 95% confidence intervals will be presented.

Timing to diagnosis of cirrhosis will be calculated from date of randomisation to the date the patient is diagnosed as having cirrhosis (in clinic) either by, in the ELF arm, having an ELF score ≥ 9.5 or in the control arm, via standard methods. Cox regression analysis, adjusting for the minimisation factors (see section 12.2), will be used to compare the differences between the survival curves, which will be calculated using the Kaplan-Meier method. Hazard ratios and corresponding 95% confidence intervals will be presented.

Detection and timing of complications of cirrhosis will be calculated from the date of diagnosis of cirrhosis, to the detection of the first event. An 'event' in this instance encompasses small and large varices, treatable HCC and inoperable HCC. Cox regression analysis, adjusting for the minimisation factors, will be used to compare the differences between the survival curves. Overall survival curves will be calculated using the Kaplan-Meier method, hazard ratios and corresponding 95% confidence intervals will be presented.

Details of all causes of mortality will be collected and documented, specifically including the number of deaths and whether or not they are suspected to be related to any treatments/trial procedures. All liver-related mortalities will be summarised separately.

Details of the economic evaluation of the ELF test are given in Section 16.

For Quality of Life (QoL), we will look at the difference in expected quality-adjusted survival to final follow-up using the Cox proportional hazards model. We will examine the impact of missing data using a Multiple Imputation method.

The proportion of non-randomised patients (where ELF < 8.4 indicating minimal/mild liver fibrosis) who go on to develop cirrhosis during the follow-up period will be summarised in order to assess false-negative rates (see section 6.3).

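### Kaplan-Meier curves overstate the cumulative incidence of severe complications and cirrhosis diagnosis, because competing deaths and transplantation lie outside the endpoints (minor reporting point)

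*Protocol*

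**What the plan says.** Protocol 19.2.1 names the quantity of interest: "Incidence and timing of severe complications of cirrhosis will be calculated from the date of randomisation", up to the first event. For the comparison of arms, "Cox regression analysis, adjusting for the minimisation factors (see section 12.2), will be used". For the curves, "Overall survival curves will be calculated using the Kaplan-Meier method", with hazard ratios and 95% confidence intervals. No other curve estimator is named.

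The death component in 17.1 is restricted: "Liver-related mortality. Any of the following", followed by a list of liver causes. Death from any other cause is not an event.

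Section 19.2.2 plans Kaplan-Meier curves for three more endpoints:
- severe complications counted from the diagnosis of cirrhosis;
- time to diagnosis ("Timing to diagnosis of cirrhosis will be calculated from date of randomisation to the date the patient is diagnosed");
- detection of varices or hepatocellular cancer.

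The last two contain no death at all. On deaths in general the same section says "Details of all causes of mortality will be collected and documented", with liver-related deaths summarised separately.

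Section 14.5 lists the circumstances that end follow-up, among them "Patient undergoes liver transplantation". Transplantation is not a component of the primary endpoint, although 18.1 counts it among the outcomes anticipated in patients with ELF of 9.5 or more (1.5% at 36 months).

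**The concern.** A patient who dies of a non-liver cause can no longer have a severe complication. A patient who dies of any cause before diagnosis can no longer be diagnosed with cirrhosis or have varices detected. Kaplan-Meier with these patients censored treats them as still able to have the event later. One minus the curve is then the risk in a hypothetical population in which nobody dies of anything else, and it is higher than the proportion of patients who actually have the event. Censoring at transplantation raises the same issue.

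What is at stake is the absolute incidence in each arm and the absolute difference between arms, which clinicians and the NHS would read off the curves. The upward shift is larger in the arm with more events, so it does not cancel in the difference. Three features of the protocol make competing deaths plausible: entry up to age 75 (7.1.1), a population described in 15.2.1 as heavily co-morbid, and a final primary analysis deferred to long follow-up (18.1, 19.1).

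**Working it through.** **Inputs from the protocol (18.1).** Control patients with ELF above 9.49 have a 22% event rate at 36 months. Accrual is 24 months, with 30 or 69 months of further follow-up. There are 500 patients per arm. Median event-free times are 22.5 years (control) and 39.1 years (ELF).

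**Reproducing the plan's figures.** With an exponential time to event and uniform accrual over *a* months followed by *f* months, P(event) = 1 − [exp(−λf) − exp(−λ(a+f))]/(aλ).
- λ = −ln(0.78)/36 = 0.00690 a month, so P = 0.2508 and 185 × 0.2508 = 46.4 events. The protocol states 46.4.
- The two medians give 51.0 and 30.1 events. The protocol states about 52 and 31.

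The medians are therefore a fair summary of the planned event rates.

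**Annual event rates.** λ(control) = ln 2/22.5 = 0.03081. λ(ELF) = ln 2/39.1 = 0.01773. Their ratio is 0.575.

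**Assumption.** The protocol gives no non-liver death rate. I take *m* = 1% to 4% a year, constant and equal in both arms. Transplantation is left out of the arithmetic; adding it would widen the gap.

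**Formulas.** One minus Kaplan-Meier at *T* years is 1 − exp(−λT). Cumulative incidence with competing death is λ/(λ+m) × [1 − exp(−(λ+m)T)].

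Example: control, T = 7.75 years (93 months = 24 + 69), m = 0.04.
- One minus Kaplan-Meier: 1 − exp(−0.03081 × 7.75) = 21.2%.
- Cumulative incidence: 0.03081/0.07081 × [1 − exp(−0.07081 × 7.75)] = 18.4%.

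| Time | Quantity | 1 − KM | Cumulative incidence, m = 1% to 4% | Excess (points) |
|---|---|---|---|---|
| 30 months | Control | 7.41% | 7.32% to 7.06% | 0.09 to 0.35 |
| 30 months | ELF | 4.34% | 4.28% to 4.13% | 0.05 to 0.21 |
| 30 months | Difference | 3.08 points | 3.04 to 2.93 points | 0.04 to 0.15 |
| 93 months | Control | 21.2% | 20.5% to 18.4% | 0.8 to 2.9 |
| 93 months | ELF | 12.8% | 12.4% to 11.1% | 0.5 to 1.8 |
| 93 months | Difference | 8.4 points | 8.1 to 7.3 points | 0.3 to 1.1 |

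The hazard ratio of 0.575 is the same in every row, because *m* does not enter the cause-specific event rate.

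**The case against.** The strongest reply is that the protocol plans survival curves and hazard ratios, and does not promise a cumulative incidence or a risk difference at a fixed time. Nor does it say how non-liver deaths are handled. Censoring rules can be left to the SAP, which was not available here and may settle this. That limits the point but does not remove it: 19.2.1 names incidence as the quantity and fixes Kaplan-Meier as the estimator, so the choice is already made in the protocol.

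The size is also open to challenge. The death rate is assumed, and at 30 months, where scheduled follow-up ends, the excess is negligible. Month 93 belongs to the original design. Section 18.1 says funding for the further five years is still being sought, and 19.1 leaves later analyses to the steering committee. This stands, and it is why the point is minor.

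Three stronger readings are tempting, and the documents do not support them.

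- **The primary test is invalid.** It is not. The adjusted Cox hazard ratio, read as cause-specific, is a valid comparison with competing deaths censored.
- **Inflated incidence feeds the lifetime cost model.** Section 16.3 says only that "The clinical trial outcome and resource utilisation data will be used to update the parameters" of that model; it names no Kaplan-Meier input. Section 16.1 takes within-trial life years from mortality data. A model that applies its own background mortality needs the cause-specific rate. Take control, month 93 and m = 3%. The cause-specific rate plus 3% mortality returns 19.0%, which is the actual cumulative incidence. A rate derived from that 19.0%, −ln(1 − 0.190)/7.75 = 0.0273, plus the same mortality returns 17.1%, because the deaths are removed twice.
- **The overstatement is as large as 6 points.** In control patients with ELF of 9.5 or more, one minus Kaplan-Meier at month 93 would be 47.4% against 45.8% to 41.4%. However, 19.2 plans no curve for that subgroup, and the figure extends a 36-month planning rate at constant hazard.

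**Conclusion.** The point holds as a minor reporting correction. As planned, with competing events censored, the Kaplan-Meier curves overstate actual cumulative incidence in both arms and slightly overstate the absolute benefit. In the control arm the excess is about 0.1 to 0.35 points at 30 months and 0.8 to 2.9 points at month 93. The risk difference at month 93 is overstated by 0.3 to 1.1 points.

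These sizes rest on an assumed non-liver death rate of 1% to 4% a year, equal in both arms, on constant hazards, and on the protocol's median times. The direction does not depend on the assumed rate: one minus Kaplan-Meier is too high whenever competing events occur and are censored. The primary test is unaffected, and nothing in the documents shows an effect on the economic model.

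**What to change.** In 19.2.1 and 19.2.2:
- Present Aalen-Johansen cumulative incidence curves by arm. The competing events are liver transplantation and any death outside the endpoint: non-liver death for severe complications, any death for time to cirrhosis diagnosis and for detected complications.
- Report the difference in cumulative incidence at fixed times with a 95% CI. Month 30 and the long-term horizon are natural choices.
- Keep the adjusted Cox model as the test and describe its hazard ratio as cause-specific.
- Avoid the label of overall survival for curves in which non-liver deaths are not events.

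Section 16.3 does not need to take cumulative incidence as its input. If the lifetime model applies its own background mortality, it should take cause-specific rates, and a sentence saying which quantity is used would prevent confusion.

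The cost is a wording change in the protocol or SAP and standard software. Deaths and their causes are already to be collected, and transplantation is already recognised as a reason for ending follow-up. Sample size and the primary test do not change.
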